This project will assess the EDC exposure of participants, through urine testing and self-administered journals. We will recruit up to 300 people (aged 18-40) from the existing participants from the Healthy Nevada Project. Participants' urine samples will be collected via mail-in kits that will be sent to participants. Participants will follow Million Marker's current user journey that involves the following: 1) users receive MM's test kits in the mail, 2) take a comprehensive 24-hour food and product exposure survey via the MM app, 3) collect their first void urine sample in the morning, 4) send back their samples, 5) view their personalized reports with tailored product recommendations through a secure online portal, 6) make changes to reduce their exposures, 7) test again to track/monitor/confirm EDC levels if any behavioral changes have been made.

Participants can make changes to reduce their exposures according to the recommendations in their personalized reports. Participants will receive a second test kit three weeks after getting their initial reports, and be asked to complete and ship it back within one week after receiving it in the mail. All participants will be offered the second test kits as there will always be room for chemical reduction.

Participants will fill out the System Usability Scale (SUS) to evaluate the usability of the Million Marker app and their experiences (engagement, satisfaction, and retention) upon the recipient of their reports for both rounds of testing.

References:

1. Wild, C. P. Complementing the genome with an 'exposome': the outstanding challenge of environmental exposure measurement in molecular epidemiology. *Cancer Epidemiol Biomark. Prev* **14**, 1847–50 (2005).
2. Wild, C. P. The exposome: from concept to utility. *Int J Epidemiol* **41**, 24–32 (2012).
3. Rappaport, S. M. & Smith, M. T. Environment and Disease Risks. *Science* **330**, 460–461 (2010).
4. Kelley, A. S. *et al.* Early pregnancy exposure to endocrine disrupting chemical mixtures are associated with inflammatory changes in maternal and neonatal

circulation. *Sci Rep* **9**, 5422 (2019).

5. Trasande, L. *et al.* Burden of disease and costs of exposure to endocrine disrupting chemicals in the European Union: an updated analysis. *Andrology* **4**, 565–72 (2016).
6. CDC. Bisphenol A (BPA) Factsheet. *National Biomonitoring Program* https://www.cdc.gov/biomonitoring/BisphenolA_FactSheet.html (2017).

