Clinical Trial Registration PRS Cover Page

Document:

Analysis Plan

Official Title:

Personalized Mobile Intervention to Reduce Exposure to Endocrine Disrupting Chemicals (EDCs) in Women of Child-Bearing Age and Their Partners

NCT Number:

NCT05780047

Document Date:

September 7, 2021

Analysis Plan, Sample Size and Power

This effort will be led by Million Marker's chief statistician and data scientist [name].

For our primary hypothesis (Aim 1), we will test and validate this first-of-its-kind mobile EDC reduction program (MM *Detect and Detox* kit) in a prospective longitudinal cohort intervention trial. We hypothesize that participants will have a reduction in EDC exposures after intervention.

Our **outcome variables** are concentrations of urinary metabolites of bisphenols (BPA, BPS, BPF), phthalates (MBP, MEP, MEHP, MEHHP, MECPP), parabens (methyl, ethyl, propyl and butyl paraben) and oxybenzone (BP-3) at baseline (pre-intervention) and second test (post-intervention, after using Million Marker's *Detect and Detox* kit, receiving the rest report with actionable insights). We will examine the distribution and concentrations of each of eight chemical analytes in urine to determine geometric means, medians, percentiles and ranges of exposures. We expect the creatinine-adjusted urinary concentration of these chemicals to be at log-normally distributed. We will compare the geometric means with those reported in the NHANES study. We will include BMI, age, gender, diet, education and household income as **covariates**. Participants' dietary patterns will be captured in the exposure journal prior to sample collection by looking at their consumption of packaged food and times eating out as these are important culprits of EDC exposures. Other covariates have been collected as part of their participation in the Healthy Nevada Project. We will conduct an **intent-to-treat analysis**, such that all participants will be included in the post-intervention analysis. The primary outcomes are the mean pre-post (first and second tests) differences in creatinine-adjusted concentration levels per analyte (i.e., the mean of the within-subject differences in analyte values from baseline/first test to post-intervention/ second test).

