In terms of **sample size and power**, an intervention study conducted by Harley et al.³⁷ showed statistically significant reduction in urinary metabolite concentration of similar EDCs pre-post intervention in adolescent girls (n=100). However, we did not find any analyte standard deviations (SDs) reported in Harley et al. We based our power and sample size calculations on the data from Rudel et al.,⁵² a dietary intervention to reduce EDCs (n=20), where the standard deviation of the difference in urinary metabolite concentrations before and after the intervention was 0.4. Our power calculation indicates that a sample size of 100 will provide 80% power to detect a 10% geometric mean difference in concentrations at baseline (pre-intervention) and second test (post-intervention) with a two-sided $\alpha=0.05$.

For our secondary hypothesis (Aim 2), we will assess changes in participants' environmental health literacy, attitudes, knowledge, and behaviors after using MM's products and services. We hypothesize that participants' environmental health literacy, attitudes, knowledge and behaviors will change after using MM's *Detect and Detox* kit and receiving their reports and personalized recommendations. We will first generate summary statistics on participants' responses. Changes will be calculated based on paired values of individual responses. We will analyze percentage changes by individual responses as well as response categories (attitude, knowledge and behaviors). A Chi-square goodness of fit test will be used for pre-post comparisons. For pre-post category comparisons within individual participants, the Wilcoxon rank-sum test will be used to compare the differences.

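### The stated 80% power at n=100 does not follow from the printed inputs: about 74% if 0.4 is the natural-log SD, and the scale of that SD is not given

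*SAP*

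**What the plan says.** The sample size and power paragraph of the SAP (Analysis Plan, Sample Size and Power) takes its variability from a 20-person dietary intervention study, in which "the standard deviation of the difference in urinary metabolite concentrations before and after the intervention was 0.4". It concludes that "a sample size of 100 will provide 80% power to detect a 10% geometric mean difference in concentrations at baseline" and the second test, with a two-sided alpha of 0.05. It names no test, no log base and no unit for the 0.4.

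Three other places bear on how to read this:

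- **Scale.** The outcome paragraph of the same SAP section says "We expect the creatinine-adjusted urinary concentration of these chemicals to be at log-normally distributed". It nevertheless defines the primary outcome as "the mean of the within-subject differences in analyte values from baseline/first test" to the second test, with no log transformation mentioned.
- **Direction.** Under Aim 1 the SAP says "We hypothesize that participants will have a reduction in EDC exposures after intervention". No size of reduction is given there; 10% appears only as the detectable difference in the power sentence.
- **Recruitment.** The protocol (Study Purpose and Narrative, item 2) says "We will recruit up to 300 people (aged 18-40) from the existing participants from the Healthy Nevada Project".

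**The concern.** The power sentence and the one before it supply SD, effect, sample size, alpha and power, so a reader should be able to recompute the last from the others. Doing so does not return 80%.

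This is the SAP's only calculated justification for a sample size, and it supports a primary outcome assessed analyte by analyte. If 0.4 is a natural-log SD, a non-significant analyte would be read against 80% power when the inputs give about 74%. The missing scale matters more than that gap. The same 0.4 gives very different power on different log scales, and without the scale it cannot be matched to a primary outcome defined without a log.

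**Working it through.** **Inputs.** From the SAP's sample size and power paragraph: n = 100, SD of the paired difference = 0.4, 10% geometric mean difference, two-sided alpha 0.05, stated power 80%. From its outcome paragraph: the comparison is within-subject, so the matching test is a paired (one-sample) test on differences. Assumed, because not printed: no covariate adjustment, 100 complete pairs, and each log scale in turn.

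**Formula.** Noncentrality λ = δ√n / SD. Power is the probability that a noncentral t with n − 1 = 99 df and noncentrality λ exceeds the critical value 1.984 in absolute value. The normal approximation is Φ(λ − 1.960).

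**Attempt to reproduce 80%, natural log, 10% reduction.**

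- δ = |ln 0.9| = 0.1054
- δ / SD = 0.1054 / 0.4 = 0.2634
- λ = 0.2634 × √100 = 2.634
- Normal approximation: Φ(2.634 − 1.960) = Φ(0.674) = 75.0%
- Noncentral t: **74.2%**

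**Other readings, SD exactly 0.4, n = 100, two-sided 0.05 (noncentral t).**

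| Reading of the 10% difference | δ | λ | Power |
|---|---|---|---|
| Natural log, 10% reduction | 0.1054 | 2.634 | 74.2% |
| Log difference taken as 0.10 | 0.1000 | 2.500 | 69.7% |
| Natural log, 10% increase (ln 1.1) | 0.0953 | 2.383 | 65.5% |
| log2, 10% reduction | 0.1520 | 3.800 | 96.4% |
| log10, 10% reduction | 0.0458 | 1.144 | 20.5% |

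None gives 80%. If 0.4 is in raw concentration units, the power for a geometric mean difference cannot be calculated from what is printed.

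**What would give 80% on natural log.** At n = 100 the t-test needs δ / SD = 0.2829.

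- Holding SD at 0.4: δ = 0.2829 × 0.4 = 0.1132, a reduction of 1 − exp(−0.1132) = **10.7%**.
- Holding the 10% reduction: SD = 0.1054 / 0.2829 = **0.372** or less.
- Holding both: 115 complete pairs give 79.98% and **116** give 80.3%. With a log difference of 0.10, 128 are needed.

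**Rounding.** Values from 0.35 to 0.45 print as 0.4. For a 10% reduction on natural log, power runs from 84.6% (SD 0.35) to 64.0% (SD 0.45), and the part from 0.350 to 0.372 supports 80%. On log2 the range is 99.0% to 91.7% and on log10 25.4% to 17.2%; neither contains 80%.

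**Sidedness.** A one-sided 0.05 test with a difference of 0.10 and SD 0.4 gives 79.9% at n = 100. It matches the stated figure but contradicts the stated two-sided alpha.

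**At the recruitment ceiling.** With 300 complete pairs, natural log, SD 0.4 and a 10% reduction, power is 99.5%.

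**The case against.** The strongest defence is precision. The SD is printed to one decimal, it comes from a study that cannot be checked here, and an unrounded natural-log value up to 0.372 gives the stated 80%. On that view the sentence is incompletely reported rather than wrong. This stands as far as cause goes. A reader might infer that the sponsor miscalculated, and the documents do not show that. Nor is there a basis for saying how likely a value in the lower part of the rounding interval is. But the SAP offers 0.4 as the input, and with 0.4 and the stated two-sided alpha none of the log readings tried returns 80%.

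The test is also unnamed, and the SAP lists covariates. If 0.4 were reduced by adjustment, covariates explaining 1 − (0.372 / 0.4)² = 13.5% of the variance of the difference would bring power to about 80%. The SAP does not say this was done.

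Materiality is limited. An SD estimated from 20 people is itself imprecise: assuming normality and 19 df, its 95% interval is about 0.30 to 0.58, which corresponds to power of about 93% to 43%. A 6-point gap is small beside that, and recruitment may go beyond 100. This fairly lowers the importance of the point, but it does not make the printed figure follow from its inputs.

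Three further inferences are not supported:

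- That the trial is underpowered. Up to 300 may be recruited. That is only a ceiling, so it does not establish adequacy either.
- That a 10% reduction is the hypothesis. The SAP hypothesizes a reduction of no stated size.
- That a one-sided test was used. The match at 79.9% is suggestive only, and the text says two-sided.

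**Conclusion.** The point holds in conditional form: 80% does not follow from the inputs as printed. If 0.4 is an exact natural-log SD and the test is an unadjusted two-sided paired t-test on 100 complete pairs, the power for a 10% reduction is about 74%, a shortfall of about 6 points. The equivalent statements are a detectable reduction of 10.7% instead of 10%, or 116 complete pairs instead of 100.

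Confidence is high in these conditional figures. It does not extend to the scale of the 0.4 or to the reason for the discrepancy, which the documents leave open. The effect on the trial is minor, but the sentence should be corrected because it is the only calculated support for the sample size and cannot be verified as it stands.

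**What to change.** In the SAP's sample size and power paragraph, print the scale and log base of the SD, its unrounded value, the test, and confirmation of its sidedness. Match these to the primary outcome definition, which at present mentions no log. Then restate the power that follows.

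If 0.4 is confirmed as the natural-log SD, the sentence could read: *100 participants with both tests give 74% power for a 10% geometric mean reduction and 80% power for a 10.7% reduction (paired t-test, two-sided alpha 0.05).* This wording should not be adopted before the scale is confirmed, since on another scale it would put a wrong figure into the SAP.

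The 80% can stay only if the printed unrounded SD and its scale support it with a two-sided test. For a 10% reduction by unadjusted paired t-test, that means a natural-log SD of 0.372 or less.

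The cost is SAP wording only, with a slightly less favourable stated power if 0.4 is confirmed as the natural-log SD. No recruitment beyond the existing ceiling of 300 is involved.

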The HNP is the largest community-based population health study in the world, with more than 60,000 participants. This is twenty times larger than NHANES, the largest nationwide population biomonitoring cohort. It's also the first population health study to return clinical results to study participants.

The collaboration between the Renown Institute for Health Innovation (RIHI) and Million Marker would 1) increase biomarker collection and discovery and 2) increase the exposure assessment database (both internal and external) conducted among existing and future project participants. The HNP Project would be the largest population environmental biomonitoring program in the world, and also the first one to report back the biomonitoring results. As most of Million Marker's current users are between the ages of 25-44, this collaboration may help the HNP recruit younger participants. For Million Marker, this collaboration would allow us to collect large amounts of samples/data to further improve our existing platform, enable AI-assisted exposure assessment and prediction, and drive long-term value for our users including the HNP participants.

To initiate this collaboration, we are proposing a pilot to offer our service to individuals within the participants in the HNP and/or through the Renown Healthcare system.

The aims of this pilot study are:

- 1) Test the feasibility of offering MM's service to the HNP existing and future participants
- 2) Collect pilot data and assess EDC levels among participants
- 3) Test the usability and perception of MM's service among participants
- 4) Test whether offering MM's service can lead to EDC reduction behaviors among participants

- 5) Utilize pilot study data to prepare for larger research studies and grant applications
2. *Provide a detailed narrative, non-technical description of the project and of the planned activity for the participants and/or data collection.*

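### Aim 2 applies a chi-square goodness-of-fit test to paired responses without defining the expected counts, and its hypothesis gives no favourable direction

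*SAP*

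**What the plan says.** The Aim 2 paragraph of the SAP (Analysis Plan, Sample Size and Power) covers environmental health literacy, attitudes, knowledge and behaviors.

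- **Hypothesis.** It predicts that participants' "environmental health literacy, attitudes, knowledge and behaviors will change after using MM's" kit and receiving their reports. No favourable direction is given.
- **Data.** "Changes will be calculated based on paired values of individual responses". Summary statistics are planned, and percentage changes are to be analysed for single responses and for the attitude, knowledge and behavior categories.
- **Tests.** "A Chi-square goodness of fit test will be used for pre-post comparisons". The next sentence adds a second test: "For pre-post category comparisons within individual participants, the Wilcoxon rank-sum test will be used to compare the differences".

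The paragraph does not define the expected counts, the response categories or the unit of the goodness-of-fit test. It gives no alpha and no success criterion. The two-sided 0.05 and the sample size of 100 in the same section belong to the Aim 1 power statement.

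Two other statements are directional. Protocol aim 4 is to "Test whether offering MM's service can lead to EDC reduction behaviors among participants". The SAP's Aim 1 hypothesis reads: "We hypothesize that participants will have a reduction in EDC exposures after intervention".

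**The concern.** There are two separate faults.

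**The test does not fit the design.** A goodness-of-fit test compares one sample with proportions known in advance. Aim 2 has two sets of answers from the same people. If the pre-test percentages are used as the known proportions, their sampling error is left out, which makes the test too liberal. The correlation between a person's two answers is also left out, which makes it too conservative. The net effect depends on a correlation that nobody knows at the planning stage, so the actual error rate is not controlled.

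**The hypothesis has no direction.** The goodness-of-fit statistic squares its differences and ignores the order of categories, so it cannot supply the direction that the hypothesis omits. A significant result would support the stated hypothesis whether participants improved or got worse.

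At stake is whether a significant Aim 2 result can be read as evidence that the program helped, and whether a non-significant one can be trusted.

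**Working it through.** The SAP gives no Aim 2 sample size, power or effect size, so there is no planned figure to reproduce.

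**Inputs.** From the SAP: the name of the test and the pairing. Assumed: expected counts equal to the pre-test counts, a 5% level, the item format and the pre-post correlation ρ. For the simulations n = 100 is borrowed from Aim 1; the Protocol allows up to 300 participants.

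**1. Error rate, two-category item, no true change.** Let p be the proportion giving one answer at both times.

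- Variance that the test assumes for the post-minus-pre difference: p(1−p)/n.
- Actual variance for paired samples: 2p(1−p)(1−ρ)/n.
- Ratio: 2(1−ρ). The statistic therefore behaves as 2(1−ρ) times a chi-square with 1 df.
- False-positive rate: P(χ²₁ > 3.841 / [2(1−ρ)]).

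| ρ | 3.841/[2(1−ρ)] | False-positive rate |
|---|---|---|
| 0 | 1.92 | 16.6% |
| 0.3 | 2.74 | 9.8% |
| 0.5 | 3.84 | 5.0% |
| 0.7 | 6.40 | 1.1% |
| 0.8 | 9.60 | 0.2% |

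The level is right only near ρ = 0.5.

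**2. Simulation check, n = 100.** The post answer repeats the pre answer with probability ρ and is otherwise a fresh draw from the same distribution.

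| ρ | Two categories (50/50) | Five categories | McNemar (50/50) |
|---|---|---|---|
| 0 | 17.5% | 34.5% | 4.6% |
| 0.3 | 10.9% | 18.0% | 5.0% |
| 0.5 | 6.0% | 7.1% | 5.5% |
| 0.7 | 1.4% | 0.8% | 4.6% |

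At n = 300 the pattern is the same: 17.8%, 10.9%, 5.6% and 1.4% for two categories. McNemar's test stayed between 4.3% and 5.5% across all correlations tried (0 to 0.9) and both sample sizes.

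**3. Lost power at strong agreement.** Assume n = 100, 50% favourable at baseline, 12% of participants improving and 2% worsening. The favourable proportion rises from 0.50 to 0.60, and 0.48 are favourable both times, so ρ = (0.48 − 0.50×0.60)/√(0.25×0.24) = 0.73. Simulated power is 55% for the goodness-of-fit test and 81% for McNemar's test.

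**4. Direction.** Take 100 assumed answers split 30/40/30 (unfavourable, neutral, favourable) at the pre-test.

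- Post 45/35/20 (worse): 15²/30 + 5²/40 + 10²/30 = 7.50 + 0.63 + 3.33 = 11.46.
- Post 20/35/45 (better): 10²/30 + 5²/40 + 15²/30 = 11.46.

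Both give p = 0.003 on 2 df. Likewise, for a two-category item with n = 100 and ρ = 0.5, a fall from 50% to 35% and a rise from 50% to 65% are each rejected about 87% of the time.

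**The case against.** The strongest reply is that the SAP never says the pre-test supplies the expected counts. A goodness-of-fit test of improvers against worseners at 50:50 is McNemar's test, which holds its level, and the SAP does say that changes use paired values. This stands as a limit on the claim: the error rates above are conditional on one reading. It does not rescue the text, because an analyst following it could run either test.

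The figures of 17% and 35% need zero correlation between one person's two answers, the extreme of the range. Nothing in the documents supports that value. With strong agreement the cost is lost power, not false positives.

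A reader might infer that the trial would count worsening as a success. The documents do not support that. Aim 2 has no success rule, the planned percentage changes would show direction, and a two-sided test read with its estimate is ordinary practice. Direction-blindness does not by itself inflate the error rate either. The mismatch with Protocol aim 4 also concerns behaviors only; that aim sets no direction for literacy, attitudes or knowledge.

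Finally, two-sided McNemar and Stuart-Maxwell tests are themselves blind to direction. This is correct, so changing the test cannot alone settle the second fault.

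The rank-sum test in the following sentence also ignores pairing. One edit of the paragraph can deal with both, but replacing that test would leave this one in place.

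**Conclusion.** The point holds in two parts.

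**Test.** The goodness-of-fit test is not adequately specified for paired data. On its natural reading the error rate depends on an unknown correlation and is near nominal only around 0.5. The size of the error rests on three assumptions: pre-test proportions as expected counts, a 5% level, and the item format and correlation shown. A flat statement that the 5% level fails would go too far, since Aim 2 states no level and another reading of the test is valid. The supportable statement is that the level is not assured.

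**Hypothesis.** It is worded without direction, and a significant worsening would agree with it. This is a fault of wording, not a decision rule that accepts harm.

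Aim 2 is a secondary aim of a pilot. The correction is worth making because it is cheap and names a better method.

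**What to change.** Revise the Aim 2 paragraph of the SAP as follows.

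1. Replace the goodness-of-fit test with a paired test of improved against worsened: McNemar for two-category items, and a sign test or Wilcoxon signed-rank test for ordered items or scores. Use Stuart-Maxwell only for unordered categories, described as an omnibus test.
2. State the alpha for Aim 2.
3. Fix the favourable direction of each item before data are seen, and word the hypothesis as improvement, at least for behaviors.
4. Report the percentages improved, unchanged and worsened, and the signed net change with a confidence interval. Conclude improvement only when the net shift is favourable.

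**Cost.** Minor SAP rewording and item coding; the paired responses are already planned. The Aim 2 questionnaire is not shown in the documents, so how readily each item can be given a favourable direction has to be checked against it. An unfavourable change would no longer support the hypothesis.

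### Aim 2 pre-post changes in the same people are assigned the Wilcoxon rank-sum test, which is for independent samples; a paired test such as signed-rank is needed

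*SAP*

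**What the plan says.** The point lies in the SAP's paragraph on the secondary hypothesis (Aim 2). The aim is one of change over time: "we will assess changes in participants' environmental health literacy, attitudes, knowledge, and behaviors after using MM's products and services". The data are described as paired: "Changes will be calculated based on paired values of individual responses". Two tests are then named. For the comparison of responses: "A Chi-square goodness of fit test will be used for pre-post comparisons". For the comparison within a person: "For pre-post category comparisons within individual participants, the Wilcoxon rank-sum test will be used to compare the differences".

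The design gives no second group. The SAP, under its primary hypothesis, describes a "prospective longitudinal cohort intervention trial". The Protocol's narrative description sends everyone along the same test-and-retest path: "All participants will be offered the second test kits as there will always be room for chemical reduction". Neither document defines a control arm or a subgroup contrast for Aim 2, and neither names the signed-rank test or any other paired rank test.

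**The concern.** The rank-sum test takes its null variance from two samples that are independent of each other. Here the two sets of scores come from the same people. When a person's scores are positively correlated, the difference between the two occasions varies less than the test assumes, so its p-values are too large. The cost is power: a real change in literacy, attitudes, knowledge or behaviours may be reported as not significant. It does not produce false positives.

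An analyst who follows the SAP will run the wrong test, and one who runs a suitable test will depart from the SAP.

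A lesser, conditional point concerns the goodness-of-fit test, for which the SAP states neither cells nor expected counts. If the observed baseline proportions serve as the expected values, the test ignores both the pairing and the sampling error in baseline, and it can then give false positives. If it sets improved against worsened responses with an expected 1:1 split, it is valid.

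**Working it through.** **1. What the documents fix.** The data are paired (SAP, Aim 2), there is one cohort (SAP, Aim 1; Protocol narrative), and the test named is rank-sum (SAP, Aim 2). The plan states no Aim 2 sample size, power, effect or SD, so there is no Aim 2 figure to reproduce.

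**2. What has to be assumed.** The pre-post correlation, the size of the shift and the item format are assumptions. Two-sided 5% and n = 100 are borrowed from Aim 1; n = 300 is the Protocol's recruitment ceiling.

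**3. Type I error by formula.** With equal numbers on both occasions and correlation ρ between a person's two scores, the true variance of the rank-sum statistic under no change is about (1 − ρ) times the variance that the test uses. The true error rate is therefore about

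2 × [1 − Φ(1.96 / √(1 − ρ))].

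- ρ = 0: 1.96 / 1 = 1.96, giving 5.0%.
- ρ = 0.3: 1.96 / √0.7 = 2.34, giving 1.9%.
- ρ = 0.5: 1.96 / √0.5 = 2.77, giving 0.56%.
- ρ = 0.7: 1.96 / √0.3 = 3.58, giving 0.03%.

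Strictly, ρ here is the correlation of the ranks, which for normal scores is a little below the ordinary correlation. The simulated rates are accordingly slightly higher at 0.3 to 0.7.

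**4. Simulation.** Bivariate normal scores, 20,000 datasets per setting, normal-approximation p-values, nominal two-sided 5%, n = 100 pairs:

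| Correlation | Rank-sum type I error | Rank-sum power, 0.3 SD shift | Signed-rank power, 0.3 SD shift |
|---|---|---|---|
| 0 | 5.0% | 54% | 54% |
| 0.3 | 2.0% | 55% | 69% |
| 0.5 | 0.7% | 56% | 83% |
| 0.7 | 0.06% | 57% | 96% |

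A separate run of 10,000 datasets put the signed-rank type I error between 4.7% and 5.0% at these correlations. With five-level ordinal scores (4,000 datasets) the pattern is the same: at correlation 0.5, rank-sum type I error is 0.7%, and power for the same shift is 51% against 78%.

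At n = 300 the rank-sum type I error is practically unchanged. For a 0.2 SD shift, power is 73% against 92% at correlation 0.5 and 78% against 99% at 0.7. For 0.3 SD the loss is at most about 2 points.

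**5. The goodness-of-fit test, if baseline proportions are the expected values.** For a binary item with pre-post correlation φ, the difference in proportions has a variance about 2(1 − φ) times what the test assumes, so the error rate is about 2 × [1 − Φ(1.96 / √(2(1 − φ)))]. At φ = 0 this is 1.96 / √2 = 1.39, or 16.6%. Simulated error rates at n = 100, from a latent normal score cut into equally likely categories:

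| Latent correlation | 2 categories | 3 categories | 5 categories |
|---|---|---|---|
| 0 | 18% | 23% | 34% |
| 0.5 | 10% | 15% | 26% |
| 0.7 | 6% | 10% | 20% |
| 0.9 | 1.3% | 3.3% | 10% |
| 0.95 | 0.2% | 1.1% | 4.5% |

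The error can thus go either way, depending on the number of categories and the correlation. At n = 300 the rates are within about 2.5 points of these. On the other reading, improved against worsened at 1:1, the error rate was 4.3% to 5.4% in all 36 settings tried.

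**The case against.** The naming error itself is hard to dispute. The fair objections are about scope and weight.

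- **It is probably a slip for signed-rank.** That is likely, but nothing in either document corrects it, so it needs correcting.
- **Signed-rank is not the only valid choice.** This stands. A sign test, a paired t-test on category scores or a mixed model would also respect the pairing; signed-rank is simply the closest replacement.
- **The sentence can be read differently.** It might mean comparing the changes across the attitude, knowledge and behaviour categories within a person. Rank-sum would still be wrong, since those changes are also dependent. But three related measures would then need something like a Friedman test or specified pairwise contrasts, so swapping one word would not be enough on that reading.
- **The Protocol sentence on second kits concerns urine testing.** Correct. It shows that there is no parallel arm; the pairing of the Aim 2 responses rests on the SAP's own statement.
- **The sizes are illustrative, and zero correlation is unlikely.** This also stands. The documents give no Aim 2 inputs. The highest goodness-of-fit error rates need zero correlation, which is implausible when the same people answer the same items. The SAP's reference to paired values just before that test also favours the valid reading. That part is a request for clarification.

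**Conclusion.** The concern holds. The SAP names an independent-samples test for what it describes as paired data, and the documents supply no second group to which that test could apply. Confidence in this is high.

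The consequence is lost power in the Aim 2 hypothesis tests. Its size rests on assumed correlations and shifts: none at zero correlation; 27 points (83% − 56%) at correlation 0.5 with 100 pairs and a 0.3 SD shift; 19 points (92% − 73%) at the same correlation with 300 pairs and a 0.2 SD shift. The Aim 2 summary statistics and percentage changes are untouched, as is the primary urinary outcome.

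The goodness-of-fit point is held with moderate confidence, because it depends on how an undefined test is read; alone it would count only as missing detail. This is a secondary hypothesis in a pilot, so the point should be fixed but does not threaten the study.

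**What to change.** - **Rank test.** Replace rank-sum with signed-rank for within-participant category scores, and state how zero differences are handled. State that the comparison is before against after within each category. If changes are instead to be compared across categories, say so and name a test for related measures.
- **Item-level test.** State the response format first. Then either use McNemar's test for binary items, signed-rank for ordinal items and Stuart-Maxwell for unordered items with several categories, or state that goodness of fit is applied to improved against worsened responses with an expected 1:1 split.

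**Cost.** One word for the rank test on the before-after reading, a short statement on zeros, and one or two sentences for the item-level test. No new data are needed. There are small downsides: signed-rank assumes roughly symmetric differences and gives no weight to unchanged scores; Stuart-Maxwell ignores category order and can fail with sparse categories; the 1:1 test ignores the size of a change.
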